Targeted Physical Examination	X				X	
Vital Signs	X					
Assessment of Signs and Symptoms	X				X	
Compression Ultrasound Doppler (CUS) evaluation	X					
Echocardiography evaluation	X					
Pregnancy test	X					
D-Dimer Test	X	X				
Follow up every 3-6 Months until 18 months		X	X	X		
Clinical Drug Supplies						
Dispense Study Treatment			X			From the first

Procedure	Screening Visit (T0)	D-Dimer test T1, T2, T3			Last Visit	Notes
		Patient with negative D-Dimer	Patient with positive D-Dimer	Patient with positive D-Dimer who refuse Apixaban		
						positive D-Dimer test Apixaban will be dispensed every 6 months
Efficacy End Points						
Primary		X	X	X	X	
Secondary		X	X	X	X	
Safety End Points						
Primary		X	X	X	X	
Secondary		X	X	X	X	

STATISTICAL CONSIDERATIONS

The aim of this management study is to demonstrate that in patients with a first unprovoked VTE a combination of a prediction rule based on D-dimer and low-dose DOAC in those at higher recurrence risk result in a recurrence risk comparable to the population of patients with provoked VTE.

Assumptions

based on the results of the DULCIS study¹⁰, approximately 45% of all eligible patients are expected to discontinue anticoagulation, with an annual rate of recurrent VTE events around 3% (95% 2.0 to 4.4%).

In the remaining 55% of patients who will be encouraged to use apixaban, based on the results of the Amplify Extension study the expected rate of recurrent VTE is around 1.7% after the first year of treatment.

Based on the metanalysis¹² the annual recurrence risk in patients with provoked VTE is 3.3%

Based on these assumptions, we expect the recurrence rate at 12 months to be:

$$0.45*0.03+0.55*0.017=2.2\%$$

Sample size: With an expected annual recurrence rate of 2.2% in the APIDULCIS population, we calculated the sample size to demonstrate, with an 80% power, that the 95% CI is below 3.5% according to Shen¹². The required sample size is 1148 patients to be recruited for the purpose of the APIDULCIS study.

Kaplan–Meier survival curves will be plotted to estimate the cumulative incidence of symptomatic recurrent VTE; hazard ratios (HR) and their 95% confidence intervals (CI) will be calculated for subgroup analyses.

Safety end-points and interim analysis

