
Statistics:
	
The aim of this management study is to demonstrate that in patients with a first VTE a combination of a prediction rule based on D-dimer and low-dose DOAC in those at higher recurrence risk result in a recurrence risk comparable to the population of patients with provoked VTE.
 
Based on assumption, we expect the recurrence rate at 12 months to be:
 
$0.45 \times 0.03 + 0.55 \times 0.017 = 2.2\%$
 
Based on the aim of the study, that the rate of recurrence should be comparable, a rate estimate with sufficient precision is only necessary and there is no need to conduct hypothesis testing. The upper limit of the 95% CI can be below 0.035 for around 800 subjects given observed $p=0.022$.
 
Kaplan–Meier survival curves will be plotted to estimate the cumulative incidence of symptomatic recurrent VTE; hazard ratios (HR) and their 95% confidence intervals (CI) will be calculated for subgroup analyses.
 
Safety end-points and interim analysis
 
Based on a 2.2% annual event rate, a total sample size around 1150 patients and 18 months of follow-up, we expect around 38 recurrences and 2 major bleeding in our study. Since low-dose apixaban may be considered as the treatment gold-standard at the time of release of the study protocol, we plan an interim analysis when 20 primary endpoints are registered. The study will be interrupted if the relative risk of primary endpoints (HR) in the observational non-treatment arm will be >3 HR, with a p value <0.0001.

Study Drug/Treatment: Apixaban

Study drugs: Apixaban 2.5 mg

The drugs will be provided by BMS.

The investigated drug is Apixaban 2.5 mg, a film coated tablet. It should be administered orally, every day BID.

The treatment should be performed for all the treatment period. Drug product is to be stored according to labeled storage conditions.

Patients who continue or resume anticoagulation will receive Apixaban 2.5 mg BID for 18 months

SAFETY AND REPORTING

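### The 80% power for 1148 patients fits a one-sided 95% upper limit; read as an ordinary two-sided 95% CI, the stated criterion has about 68–75% power

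*Protocol*

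**What the plan says.** Statistical Considerations, Sample size, starts from the planning rate ("With an expected annual recurrence rate of 2.2% in the APIDULCIS population") and sizes the study to show "with an 80% power, that the 95% CI is below 3.5" per cent, citing a published method for controlling the upper confidence limit of a binomial rate. It concludes: "The required sample size is 1148 patients to be recruited for the purpose of the APIDULCIS study".

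The Statistics entry of the Protocol Synopsis uses the same planning rate but takes a different line. It says that "a rate estimate with sufficient precision is only necessary and there is no need to conduct hypothesis testing", and then: "The upper limit of the 95% CI can be below 0.035 for around 800 subjects given observed" a proportion of 0.022. It attaches no power to that number.

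Neither place says whether the 95% CI is one- or two-sided, or how it is to be computed. The one other interval printed in the section, for the earlier management study ("with an annual rate of recurrent VTE events around 3% (95% 2.0 to 4.4" per cent), has a lower and an upper end.

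**The concern.** The 3.5% bound is the only numerical success criterion in the protocol. It carries the claim that recurrence under this strategy is comparable to that after provoked VTE. An unqualified 95% CI is normally read as two-sided, so its upper end leaves 2.5% in the tail. A one-sided 95% limit leaves 5%. It is the upper end of a two-sided 90% CI and is easier to bring below 3.5%.

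If the sample size rests on one limit and the results are judged by the other, the printed power does not belong to the printed criterion. There is also a narrow band of results in which the choice of limit decides whether the study succeeded, and that choice should not be open once the data are known. The figure of around 800 under the same label adds to the doubt about which limit is meant.

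**Working it through.** **Inputs, all from Statistical Considerations:** p1 = 0.022 (expected rate, taken as printed), p0 = 0.035 (bound), d = p0 − p1 = 0.013, power 80% (z = 0.8416). Sidedness is not given, so both readings are computed. Each patient is treated as having a complete 12-month yes/no outcome.

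**1. Reproducing 1148.** One-sample binomial formula with continuity correction:

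n = [z_a·√(p0(1−p0)) + z_b·√(p1(1−p1))]² / d²

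n_cc = (n/4)·[1 + √(1 + 2/(n·d))]²

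with √(0.035·0.965) = 0.18378 and √(0.022·0.978) = 0.14668.

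- One-sided 95% (z_a = 1.645): n = (0.3023 + 0.1234)²/0.000169 = 1072.5. Then n_cc = 268.13 × (1 + √1.1434)² = **1148.2**.
- Two-sided 95% (z_a = 1.960): n = (0.3602 + 0.1234)²/0.000169 = 1384.1. Then n_cc = 346.04 × (1 + √1.1112)² = **1460.1**.

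The printed number matches the one-sided version to the patient.

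**2. Power at the sizes the protocol names.** For each n, find the largest event count whose Clopper–Pearson upper limit is below 3.5%, then take the binomial probability of that count or fewer. Wilson limits allow the same counts. The size 1150 comes from the interim analysis section and 1,200 from the synopsis accrual goal.

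| n | Limit | Events allowed | Power at 2.2% | False success at 3.5% |
|---|---|---|---|---|
| 1148 | one-sided 95% | 29 | 80.6% | 3.8% |
| 1148 | two-sided 95% | 27 | 68.3% | 1.7% |
| 1150 | two-sided 95% | 28 | 74.6% | 2.5% |
| 1200 | two-sided 95% | 29 | 73.6% | 2.0% |

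At n = 1148, 29 events give a one-sided upper limit of 3.43%. Under the two-sided limit, 27 events give 3.40% and 28 give 3.506%. So 28 or 29 events would pass one reading and fail the other; the probability of that at 2.2% is 80.6% − 68.3% = 12.3%.

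Two-sided power moves in a sawtooth because the allowed count changes in whole events. Between 1148 and 1200 it runs from 68.2% (n = 1149, 27 events) to 75.8% (n = 1184, 29 events) and never reaches 80%.

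**3. The synopsis figure of around 800.** Holding the observed proportion at 0.022, the smallest n whose upper limit is below 3.5% is:

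- two-sided 95%: 772 (Clopper–Pearson) or 768 (Wilson); at n = 800 the exact limit is 3.47%;
- one-sided 95%: 573 or 541; at n = 800 the exact limit is 3.26%.

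A third route also comes close. The simple one-sided Wald formula at 80% power gives (1.645 + 0.8416)² × 0.022 × 0.978/0.000169 = 787.

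**The case against.** **A one-sided limit may have been intended.** The cited method, by its title, concerns the upper confidence limit. On that reading 1148 is correct and there is no arithmetic error. This stands. The remaining defect is the label, since an unqualified 95% CI does not describe that limit.

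**A two-sided Wald interval would restore the power.** At 1148 it allows 29 events and so gives 80.6%. But its false-success rate at 3.5% is then 3.8% against a nominal 2.5%. Its closed form gives 999 rather than 1148, and it would need only about 490 patients for the synopsis statement. It explains neither printed number.

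**68% is a low point of the sawtooth.** This also stands. Two more patients raise it to 74.6%, so the fair statement is a range.

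**Stronger readings that a reader might infer.** One is that the protocol demonstrably sized 1148 on a one-sided limit and 800 on a two-sided one. The wording about an observed 0.022 favours the two-sided precision reading, but 800 is rounded and the one-sided 787 lies nearer to it than 772 does, so its origin is not established. Another is that the same data could pass the body's rule and fail the synopsis's rule. The synopsis sets no pass/fail rule and disclaims testing. A third is that the study is too small and needs about 1460 patients. That follows only if both the two-sided CI and 80% power must be kept.

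**The SAP may settle it.** The interval method can properly sit there. But the protocol itself prints a criterion, a power and a number of patients that do not agree under the usual meaning of 95% CI. The interval from the earlier study and the subgroup hazard-ratio intervals do not fix the sidedness of the primary criterion either way.

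**Conclusion.** The point holds as a mismatch between label and calculation. 1148 patients with 80% power fits a one-sided 95% upper limit. Read as an ordinary two-sided 95% CI with exact or score limits, the same criterion has 68–75% power at the three sizes the protocol names, a shortfall of roughly 5 to 12 percentage points. With the one-sided limit the power is about 80% and the false-success rate at a true 3.5% is about 4%.

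This rests on three assumptions: the printed 2.2% and 3.5%, complete 12-month outcomes, and sidedness inferred from reproducing the figure, because the protocol does not state it. For the figure of around 800, the documents support only that its basis is unexplained and that it should not share a label with 1148 unexplained.

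**What to change.** State one criterion for the 12-month recurrence rate, in the same words, in the Sample size paragraph and in the synopsis Statistics entry. Either:

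- define success as the upper one-sided 95% confidence limit (equal to the upper end of the two-sided 90% CI) lying below 3.5%, and keep 1148 with 80% power; or
- keep the two-sided 95% CI and restate the power as about 68–75%, calculated for the number expected in the analysis.

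Name the interval method. Delete the figure of around 800, or recompute it on the chosen limit and label it a precision statement: with exact limits at an observed 2.2% it is 573 one-sided or 772 two-sided.

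Do not write a bare event count into the rule. The 27 and 29 above belong to a 12-month rate in exactly 1148 patients. The protocol expects about 38 recurrences over 18 months (1150 × 0.022 × 1.5 = 37.95), plans Kaplan–Meier estimation and aims to accrue 1,200. A count is safe only if tied to the 12-month horizon and to the number actually analysed.

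The cost is a few sentences and no extra patients. The price is either a lower stated power or an openly one-sided claim.

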 - ✓ current or recent gastrointestinal ulceration, presence of malignant neoplasms at high risk of bleeding, recent brain or spinal injury, recent brain, spinal or ophthalmic surgery, recent intracranial hemorrhage, known or suspected esophageal varices, arteriovenous malformations, vascular aneurysms or major intra-spinal or intracerebral vascular abnormalities;
 - ✓ concomitant treatment with any other anticoagulant agent e.g., unfractionated heparin (UFH), low molecular weight heparins, heparin derivatives (fondaparinux, etc.), oral anticoagulants (warfarin, rivaroxaban, dabigatran, etc.) except under specific circumstances of switching anticoagulant therapy or when UFH is given at doses necessary to maintain an open central venous or arterial catheter.

The patients with one of the absolute contraindications to Eliquis are invited to resume anticoagulation using a different anticoagulant drug.

FOLLOW-UP AND STUDY END-POINTS

All patients included in the study, a) those with persistently negative D-dimer who stopped anticoagulation, b) those with positive D-dimer who continued or resumed anticoagulant treatment by assuming apixaban 2.5 mg BID, and c) those with positive D-dimer who may refuse to assume apixaban as well as any other anticoagulant or antithrombotic agent for secondary VTE prevention, will be followed up for at least 18 months after recruitment in the study. They will be examined or interviewed telephonically every 3-6 months in order to assess their health conditions and to check the occurrence of events. All primary events occurring during the follow-up, including objectively proven recurrent VTE, major or clinically relevant non-major bleedings and deaths from any cause will be objectively documented according to widely accepted guidelines and recorded. All the events will be adjudicated by a central adjudication committee. All the patients are invited to immediately refer to the enrolling center at the appearance of signs or symptoms compatible with venous thromboembolism or other complications (such as bleeding episodes).

Primary efficacy end-point: the composite of confirmed recurrent VTE and VTE-related death occurring during follow-up in all included patients

Primary safety end-point: major bleeding ¹¹ complications occurring during the follow-up period in all included patients

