Based on a 2.2% annual event rate, a total sample size around 1150 patients and 18 months of follow-up, we expect around 38 recurrences and 2 major bleeding in our study. Since low-dose apixaban may be considered as the treatment gold-standard at the time of release of the study protocol, we plan an interim analysis when 20 primary endpoints are registered. The study will be interrupted if the relative risk of primary endpoints (HR) in the observational non-treatment arm will be >3 HR, with a p value <0.0001.

PROTOCOL SYNOPSIS

Title:	APIDULCIS: Extended anticoagulation with low-dose apixaban after a standard course anticoagulation in patients with a first venous thromboembolism who have positive D-dimer
Country:	Italy
Number of Sites:	53 centers
Research Hypothesis:	
The cumulative incidence of VTE recurrence 10 years after stopping anticoagulation is about 50% and 20% after a first unprovoked and provoked event respectively. It is not related to the duration of anticoagulant treatment. In addition, the rate of fatal bleeding on indefinite treatment is comparable to that of fatal PE in patients with anticoagulation discontinuation, and the case-fatality rate of major bleeding is higher than that of symptomatic recurrent events
 
The latest ACCP international guidelines suggest an indefinite duration of anticoagulation in all patients after an unprovoked event, at low or moderate risk of bleeding. All the available evaluations derive from studies on vitamin K antagonists (VKA) treatment. The use of the novel direct oral anticoagulants (DOACs) offers a valid alternative to vitamin k antagonist and in particular, for the extended treatment, low-dose apixaban (2.5 mg BID) proved effective with better safety results than VKA.
 
The DULCIS management study showed that in VKA patients with an unprovoked (or associated with a weak risk factor) symptomatic episode of proximal DVT, serial D-dimer measurement with the assessment of residual thrombosis allows to detect those VTE patients at low recurrence risk (annual rate, 3.0%) who can discontinue anticoagulation.
 
The latest ACCP guidelines suggest the use of D-dimer assessment after stop anticoagulation to decide the extended treatment.

Study Schema: Drugs / Doses / Length of Treatment)	Apixaban 2.5mg Treatment: 18 months

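### The interim stopping rule tests a hazard ratio between D-dimer-defined groups, sets no absolute limit for untreated patients, and at 20 events needs an observed HR of about 11, not 3

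*Protocol*

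**What the plan says.** The rule stands in the Protocol under *Safety end-points and interim analysis* and is repeated in the Synopsis (*Statistics*). The Synopsis row on criteria for evaluation refers to it for stopping rules, and no other study-level stopping rule appears.

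- Timing: "we plan an interim analysis when 20 primary endpoints are registered".
- Boundary: "The study will be interrupted if the relative risk of primary endpoints (HR) in the observational non-treatment arm will be >3 HR", with p below 0.0001.
- Reason given: "Since low-dose apixaban may be considered as the treatment gold-standard at the time of release of the study protocol". The rule names no reference group; apixaban-treated patients are inferred from this sentence.

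Under *D-dimer assessment*, treatment is not randomised. Persistently negative patients stay off anticoagulation and positive patients are offered apixaban. D-dimer-positive patients who refuse treatment are also followed, and the rule does not say whether they belong to the non-treatment arm.

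The planning rates are under *Statistical considerations*. For untreated patients: "approximately 45% of all eligible patients are expected to discontinue anticoagulation, with an annual rate of recurrent VTE events around 3" per cent, with a range of 2.0 to 4.4%. For apixaban: "the expected rate of recurrent VTE is around 1.7% after the first year of treatment". The same section gives 3.3% a year for provoked VTE and a 3.5% ceiling for the upper confidence limit in the whole study population.

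**The concern.** The rule is the only formal study-level protection for patients taken off anticoagulation. What matters for them is how often they recur, and the aim of the study (whether extended anticoagulation can be safely avoided in a low-risk subset) is put in those terms. The rule looks at a ratio instead.

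The two groups are separated by the study's own predictor of recurrence, so the ratio does not estimate the effect of withholding apixaban from D-dimer-negative patients. It also moves with the apixaban rate: high rates in both groups give an unremarkable HR, and a very low apixaban rate inflates it.

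The two parts of the boundary also look incompatible at 20 events, since p<0.0001 may demand a far larger ratio than 3. If so, the rule offers much less protection than its wording suggests.

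**Working it through.** **Inputs from the Protocol.** 20 events; HR >3 and p<0.0001; groups of 45% and 55%; planned rates of 3.0% and 1.7% a year; about 1150 patients followed for 18 months.

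**Assumptions.** Person-time splits 45:55, rates are constant, the events are those of the primary efficacy end-point, and the comparator is apixaban. Rates other than 3.0% and 1.7% are illustrative, except 4.4%, the top of the protocol's range.

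**The plan's own figure.** 1150 × 0.022 × 1.5 = 37.95, which reproduces the stated 38 recurrences. The weighted sum 0.45 × 3.0 + 0.55 × 1.7 is 2.285%, so 20 events are expected after 20 / 0.02285 = 875 of about 1150 × 1.5 = 1725 person-years. The planned HR is 3.0 / 1.7 = 1.76.

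**Step 1: what p<0.0001 requires.** With equal rates, untreated events among the 20 follow Binomial(20, 0.45). The observed HR is (k/0.45) / ((20−k)/0.55).

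| Split (untreated : apixaban) | Observed HR | One-sided exact p | Two-sided score p |
|---|---|---|---|
| 15:5 | 3.67 | 0.0064 | 0.0070 |
| 17:3 | 6.93 | 0.00028 | 0.00032 |
| 18:2 | 11.0 | 0.000036 | 0.000052 |

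Doubling the one-sided exact p gives 0.00055 at 17:3 and 0.000072 at 18:2, so the boundary is 18:2 on each of these tests. A Wald test on the log HR, with variance 1/k + 1/(20−k), does not reach 0.0001 at any split from 10:10 to 19:1.

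**Step 2: chance of stopping.** For an untreated rate u and apixaban rate t, each event is untreated with probability q = 0.45u / (0.45u + 0.55t). The chance of stopping is P(Bin(20, q) ≥ 18), given that 20 events are reached.

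| u / t (% per year) | True HR | q | P(stop) |
|---|---|---|---|
| 3 / 1.7 (planned) | 1.76 | 0.591 | 0.3% |
| 3 / 1 | 3.0 | 0.711 | 4.4% |
| 6 / 1.7 | 3.5 | 0.743 | 8% |
| 10 / 1.7 | 5.9 | 0.828 | 31% |
| 15 / 1.7 | 8.8 | 0.878 | 55% |
| 10 / 5 | 2.0 | 0.621 | 0.6% |
| 3 / 0.5 | 6.0 | 0.831 | 32% |

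At a true HR of 3, the Schoenfeld approximation gives 7% rather than 4.4%. By the same formula, 80% power at that HR needs (3.891 + 0.842)² / (0.45 × 0.55 × (ln 3)²) ≈ 75 events, against 38 expected in the whole study.

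**Step 3: an absolute criterion at the same look.** Total person-time at the 20th event was simulated as Gamma(20, pooled rate), with 45% of it untreated. The illustrative rule stops if the lower exact Poisson 95% limit of the untreated rate exceeds a chosen limit.

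| u / t (% per year) | Limit 3.5% | Limit 4.4% | Rule as written |
|---|---|---|---|
| 3 / 1.7 | 0.7% | 0.1% | 0.3% |
| 4.4 / 1.7 | 11% | 2% | 2% |
| 5 / 1.7 | 22% | 6% | 4% |
| 6 / 1.7 | 46% | 18% | 8% |
| 10 / 1.7 | 97% | 86% | 31% |

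**The case against.** **A relative rule has a rationale.** If apixaban is the standard, it is fair to ask whether untreated patients do far worse than concurrent treated ones. D-dimer-negative patients are expected to have the lower underlying risk, so a large HR against them would be a genuine warning. This stands as a reason to report the HR. It does not make the HR a measure of untreated risk.

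**A strict p value is common at an interim look.** It is normally used to protect the final test. Here the final criterion is a confidence limit on the pooled rate, not this HR, so the strictness protects no final comparison while making the printed threshold of 3 irrelevant.

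**A reader might infer that the rule is more likely to stop when untreated patients do well than when they do badly.** The documents do not support that. It appears only when both rates are changed together. With apixaban held at the planned 1.7%, stopping rises from 0.3% at an untreated 3% to 55% at 15%: the rule is weak but points the right way. A stop with untreated patients at 3% needs an apixaban rate far below plan, and the 32% at 3% against 0.5% is conditional on reaching 20 events, which takes about 20 / 0.01625 = 1231 person-years.

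**A reader might also take 3.5% as the ready-made limit for untreated patients.** The Protocol sets it for the pooled population, and it lies inside the 2.0 to 4.4% range quoted for the untreated group. At 5% against 1.7% the pooled rate is 0.45 × 5 + 0.55 × 1.7 = 3.19%, below 3.5%, yet a 3.5% limit on the untreated group would stop 22% of the time.

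**Some details may be in the SAP.** The test, its sidedness and the place of refusers could be settled there. The measure, the event count and both thresholds are fixed in the Protocol, and the finding rests on those.

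**Conclusion.** The concern holds. The only study-level stopping rule uses a ratio between groups formed by D-dimer and includes no absolute rate for the patients it is meant to protect. Its two conditions do not fit together: at 20 events p<0.0001 demands an HR of about 11, so HR >3 is inoperative.

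The failure to detect harm is the stronger half. With apixaban exactly as planned, an untreated rate of 10% a year, more than three times the 3.0% benchmark, goes unstopped about 69% of the time, and almost always if apixaban also does badly. The false-stop half is real but conditional on apixaban doing much better than assumed.

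The figures rest on the 45:55 split, constant rates, exactly 20 events and an inferred apixaban comparator. The 18:2 boundary does not depend on the illustrative rates. This should be corrected; it does not affect the validity of the primary estimate.

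**What to change.** Keep the look at 20 events, defined as adjudicated recurrent VTE or VTE-related deaths. The definition needs stating because *Follow-up and study end-points* uses primary events more widely: "All primary events occurring during the follow-up, including objectively proven recurrent VTE, major or clinically relevant non-major bleedings and deaths from any cause". Replace the HR and p value condition with a criterion on the annual recurrence rate, with exact confidence interval, in untreated D-dimer-negative patients. Report the HR descriptively, and show D-dimer-positive refusers and bleeding separately.

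The sponsor should set the limit for this group explicitly and reconcile it with the Protocol's 3.0% (2.0 to 4.4%), 3.3% and 3.5% figures. The pooled 3.5% should not be carried over without justification. State the operating characteristics of the chosen limit in the form of the last table above, where 3.5% and 4.4% are illustrations only.

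The cost is one rewritten paragraph, repeated in the Synopsis, with the same data and timing. The downside is a modest chance of stopping when the untreated rate is moderately above plan and the pooled target would still be met. How much of that to accept is the sponsor's judgement.
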